This is a multi-center RCT. We will enroll 48 participants (24 per site). Participants will be randomized to receive either PT3 or the comparison intervention. We will employ a randomized block design with two blocking factors, GMFCS level and study site. This will address any clinical heterogeneity of outcome measures by functional level and study site. Outcomes assessors will be blinded to group assignment. The study biostatistician, [name], will generate randomization sequences in accordance with the study design.

Recruitment

Participants will be recruited from the local hospitals and physical therapy clinics. Colleagues will be sent emails and/or letters describing the purpose of the study and criteria and asking them to share the study

information and my contact information with their patients. IRB-approved letters of support from colleagues, study flyer, and a provider approach template letter will be utilized for recruitment.

Identification of potential participants may also occur through the Louisiana Children's Medical Center electronic medical record (EMR) system known as EPIC in conjunction with Children's Hospital New Orleans (CHNOLA). A request from LSUHSC personnel will be sent to CHNOLA's Director of Research Operations using the previously mentioned inclusion criteria, desired PHI (i.e. first and last name, date of birth, address, etc.), and ICD-10 codes. The CHNOLA Director of Research Operations will create an IT Ticket and send it to EPIC to have a report generated with all requested data. After receiving PHI, LSUHSC personnel will perform a basic review of the participant's medical records to identify whether or not the participants meet basic eligibility requirements. Patients identified as a potential participant will be initially contacted by the CHNOLA Site PI (i.e. direct mail, EPIC messages, email, etc.), however all contact thereafter would be handled by the LSUHSC personnel. An approach mailing will include IRB-approved materials, including: approach letter, study flyer, return letter of interest and postage paid envelope to return letter of interest to study staff LSUHSC-NO. Approach email will include IRB-approved materials, including: approach letter, study flyer, and contact information of study staff at LSUHSC-NO.

Protocols and Timeline

Intervention Protocols:

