Fidelity of Interventions: Intervention fidelity across sites will be addressed by in-person training of all intervention therapists by [name] employing an intervention visit procedural checklist of visit tasks. Intervention therapists must reach 100% performance and completion prior to study initiation. Training videos and manuals will be provided for reference. Interventionists will complete checklist for every study visit with physical monitoring of intervention visits by the site PI at weeks 1, 4 and 7 for each participant with real-time feedback provided. If performance falls <95%, the interventionist will repeat training.

Testing / Assessment Protocols

Procedures: Outcomes will be assessed pre and post intervention to determine immediate effects of treatment; at 2 months post for short-term retention; and 6 months post for long-term retention (Figure 4). The goal will be to perform the baseline assessment within 1 week prior to the start of the intervention and within 1 week of completing the intervention for the post assessment but must always occur a minimum of 48 hours before or after a training session for baseline and post-assessment, respectively. However, a 2-week window will be allowed for all assessment timepoints.

[figure not shown]

Figure 4. Experimental design for 8-week interventions and timeline for assessment. TT = treadmill training

Outcome Measures: Assessors will be blinded to group assignment.

- 1) **Clinical Assessment:** Anthropometric measurements (height, weight, leg length, lower leg length, thigh length) will be collected. Knee and ankle range-of-motion will be measured. The child will be classified according to the Gross Motor Function Classification System (GMFCS), levels I, II, or II.

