Fidelity of Assessments (SA 1,2,3): Assessment fidelity between sites for SA1 and 3 will be addressed by in-person training of assessment therapists by [name]/[name], using consistent walk test distance metrics, demonstrated StepWatch/GPS calibration/donning, and an assessment visit procedural reliability checklist of visit tasks/tests to standard of 100%. Site PIs will monitor and confirm assessment visit fidelity at every 10th study visit (10% of visits) over the study data collection period. Ultrasound imaging fidelity (SA 2) will be addressed by real-time videoconferencing of [name] by [name] during every baseline study visit (25% of visits) and was implemented effectively with recent R21 pilot study. Fidelity of muscle performance data collection (SA 2) will be addressed between sites by in-person training by [name] at both sites and by real time PI/ per site observation every 10th visit (10% of visits) throughout the study data collection period with assessment visit procedural reliability checklist of visit tasks/tests to a standard of 100%. Training videos and manuals will be provided for reference for all of the outcome assessments. In addition to on-site training, the PI will perform site visits in Seattle every 6 months to 1 year (see timeline C.8). [name] and [name] will hold monthly conference calls to discuss study progress and any protocol deviations. The entire research team will meet quarterly using closed-circuit videoconferencing.

Risks to Participants

The risks to the subjects for the locomotor treadmill training or walking capacity/performance testing would not be greater than risk during regular physical therapy gait training sessions. Typically, ambulation on a treadmill involves a risk of tripping and falling. However, subjects will wear a gait belt with contact guard assistance by the interventionist or be connected to an overhead harness which would prevent such an occurrence. Therefore, the risk of falling associated with this experiment is minimal. This fall prevention strategy has been effectively employed within the current R21 pilot protocol (R21 HD077186-01A1) with no adverse events reported related to falls during the short-burst treadmill training. Participants will also be allowed to use the treadmill railings as need during the training.

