There is a mild risk of temporary delayed-onset muscle soreness from walking, power and strength training and testing, as well as joint pain, particularly in the knees. However, [name] has previously performed maximum strength and power testing and training protocols in the lower extremity in both CP and typically developing children populations and reports of muscle soreness or joint pain have been minimal and were reported mild to moderate in intensity. Reports of joint injury are rare. In order to minimize physical risks, these protocols have been designed according to the latest resistance training guidelines for children and adolescents put forth by the National Strength and Conditioning Association (NSCA) position papers for youth

resistance training and includes scheduling rest periods between sets and 48 hours between training sessions. If muscle soreness is reported, subjects and their parents will be instructed on basic standard of care, such as stretching, icing, and use of over-the-counter nonsteroidal anti-inflammatory medications. Participants will be monitored by the intervention research physical therapist for appropriate fatigue, muscle soreness, joint pain, falls and/or unexpected physical discomfort during intervention and testing sessions.

There is minimal risk of blisters and/or chafing associated with training equipment used during the power and strength training and testing. This is no greater risk than standard of care physical therapy where a child is administered strength training. In order to minimize the risk of blisters and/or chafing, weight-lifting gloves will be provided to all subjects during training.

There are no known risks associated with ultrasound imaging.

There is minimal risk of intolerance or skin issues with wearing of the StepWatch/GPS devices.

The questionnaires/interviews completed by the parent are solely for the research project with the level of risk considered minimal to none. If the participant were to experience any emotional sadness or discomfort as a result of the questionnaires, we would refer the parent to an appropriate health care provider, such as a counselor or psychologist.

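### The intervention therapist, who knows the allocation, is assigned to monitor children during testing sessions, leaving the stated assessor blinding unprotected at the walk tests

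*Combined protocol and SAP*

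**What the plan says.** Blinding is stated twice. Study Design and Randomization says "Outcomes assessors will be blinded to group assignment", and Outcome Measures, under Testing / Assessment Protocols, says "Assessors will be blinded to group assignment".

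Risks to Participants, in the paragraph on soreness and joint pain, sets out that each child is "monitored by the intervention research physical therapist for appropriate fatigue, muscle soreness, joint pain, falls and/or unexpected physical discomfort during intervention and testing sessions".

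Two fidelity provisions also bear on who attends. Under Fidelity of Interventions there is "physical monitoring of intervention visits by the site PI at weeks 1, 4 and 7 for each participant with real-time feedback provided". Under Fidelity of Assessments, "Site PIs will monitor and confirm assessment visit fidelity at every 10th study visit (10% of visits) over the study data collection period", with a similar provision for muscle performance testing: "real time PI/ per site observation every 10th visit (10% of visits) throughout the study data collection period".

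Self-selected gait speed is the primary outcome (Specific Aims, Aim 1). It is the average of three timed 10-metre walks done in person (Outcome Measures, Walking Capacity).

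**The concern.** The child takes part in the training and cannot be assumed blind to it, so the blinded assessor is the main protection against bias in the walk tests. The monitoring rule puts at the testing sessions a member of staff whose job involves knowing the arm. That person could encourage or cue the child, or let the assessor learn the allocation through a remark or by how they deal with the child.

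Gait speed over a short walk depends on how the child chooses to behave, and the fast walk and the 1-minute walk depend on effort. If such influence differed by arm, it would enter the primary comparison directly, and no analysis in the Data Analysis Plan could remove it.

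**Working it through.** **1. What testing sessions covers.** Three places point to the outcome visits:
- The section describing the outcome measures is headed Testing / Assessment Protocols.
- Risks to Participants opens with the risks of treadmill training and of walking capacity and performance testing, and so calls the walk assessments testing.
- The paragraph holding the monitoring rule attributes possible soreness to walking, power and strength training and also to testing.

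One place points the other way. The intervention protocols describe a separate 1RM test, at least 48 hours before the first training session, and call it a session. Nothing limits the monitoring rule to that occasion. The plain reading includes the outcome visits.

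**2. What protects the blind at those visits.** The ultrasound outcomes have a concrete safeguard: de-identified images read by a blinded assessor. For the walk tests I found no rule on who may be present, on encouragement, on keeping treating and assessing therapists apart, or on checking whether the blind held. Fidelity of Assessments names assessment therapists as a role but does not say they are kept apart from the intervention therapists.

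**3. What a bias would do (illustration only).** The plan gives no figure for this.

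Inputs from Power Calculations: n = 24 per group; two-sided 0.05; design difference 0.12 m/s; SD 0.167 m/s for self-selected speed. The SD of 0.127 m/s, given there for fast speed, is used as the lower end of a range. Assumption, not in the documents: the therapist's presence shifts the between-arm difference in change by b = 0.02, 0.03 or 0.05 m/s, at every post-treatment test. The ends are 0.02/0.12 = 17% and 0.05/0.12 = 42% of the design difference.

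With a two-sample t-test as an approximation to the planned blocked model:
- SE = SD × √(2/24), which is 0.0482 for SD 0.167 and 0.0367 for SD 0.127.
- Noncentrality λ = b/SE, with 46 degrees of freedom and critical value 2.013.
- False-positive rate = P(|T| > 2.013), where T is noncentral t with parameter λ and there is no true effect.

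| b (m/s) | λ, SD 0.167 | Error rate | λ, SD 0.127 | Error rate |
|---|---|---|---|---|
| 0 | 0 | 5% | 0 | 5% |
| 0.02 | 0.41 | 7% | 0.55 | 8% |
| 0.03 | 0.62 | 9% | 0.82 | 13% |
| 0.05 | 1.04 | 17% | 1.36 | 27% |

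The row b = 0 also covers a therapist whose presence affects both arms equally, because a common shift cancels in the difference.

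**4. The site PI's attendance.** Planned assessments number 48 × 4 = 192, and 10% of them is about 19. If these are spread evenly, 48 × 0.10 is about 5 of the 48 immediate post-treatment visits. The same assumed shifts confined to 10% of visits average 0.002 to 0.005 m/s and leave the error rate at 5.0-5.2%.

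**The case against.** **The text may mean less.** The rule sits in a paragraph on soreness and joint pain, the 1RM test is called a session elsewhere, and outcome visits are mostly called assessment visits. The sponsor may have meant 1RM testing only. That stands as a possibility, but the document does not say so, and its own headings favour the wider reading.

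**A role is named, not a person or a task.** A reader might infer that the child's own trainer stands beside the walkway or times the walk. The text supports neither. It names the intervention therapist role, the fidelity section refers to intervention therapists in the plural, and soreness could be asked about before or after a test. This stands, and it limits the point to an unprotected risk.

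**Monitoring is the same in both arms.** Presence alone creates no between-arm bias; differential cueing or disclosure is needed. The primary outcome is also a comfortable-speed walk, not a maximum-effort test. Both points stand, and they are why the error rates above are conditional.

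**The site PI.** Because of "physical monitoring of intervention visits by the site PI at weeks 1, 4 and 7 for each participant" and "Site PIs will monitor and confirm assessment visit fidelity at every 10th study visit", a reader might infer that the site PI's attendance is an equal breach and that the fidelity checks should move to baseline. The site PI does learn the allocations, but attends about one assessment in ten, and step 4 shows a negligible effect. Moving every check to baseline would leave no walk test observed after treatment, which defeats the purpose of checking throughout data collection.

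**Conclusion.** The concern holds as an inconsistency between two rules. Assessors are to be blinded, while staff who know the allocation are assigned to monitor sessions that, on the plain reading, include the blinded outcome visits. Followed as written, the monitoring rule weakens the stated blinding of the primary and secondary walk tests.

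A reader might conclude that assessors will be unblinded, or that the trial's true error rate is as high as 27%. The documents support neither. Nobody who knows the allocation is said to time or score the walk, and the 7-17% and 8-27% ranges rest wholly on an assumed arm-specific shift of 0.02 to 0.05 m/s at every post-treatment test. The actual size is unknown and could be nil. The point merits a change because the correction is cheap and the outcome has no other stated protection.

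**What to change.** Reconcile Study Design and Randomization, Outcome Measures and Risks to Participants:

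1. In Risks to Participants, limit the intervention therapist's monitoring to training and 1RM sessions.
2. Assign the monitoring at post-baseline outcome visits to the blinded assessment therapist, or to other staff unaware of the allocation, so that the safety observation is kept.
3. Under Outcome Measures, state that therapists who know a child's allocation are not present during that child's post-baseline walk tests.
4. Keep the site-PI fidelity checks throughout the study as planned. Add only that the observer does not disclose the allocation or interact with the child during the test.

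The cost is wording, some scheduling, and an observation task for the assessment therapist. The documents do not describe staffing at assessment visits, so each site should confirm that one person can both run the walk tests and watch the child, or name a second person unaware of the allocation.

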Power Based Approach: Power training combined with interval treadmill training (PT3). Participants will receive 24, 1-hour sessions of PT3 over 8 weeks (3 x per week with minimum of 48 hours separating treatment sessions). Participants will be allowed an additional 2 weeks to make up any missed sessions for a maximum of 10 weeks to complete the 24 sessions. This protocol was based on the National Strength and Conditioning Association (NSCA) resistance training guidelines for children and adolescents for power (Faigenbaum, 2009) and on prior work. The training session will begin with a 5 minute warm-up consisting of any of the following activities, tailored to each participant: walking at self-selected speed, stationary cycling without resistance, or dynamic stretching. Training will consist of unilateral and bilateral leg presses (Total Gym GTS®, San Diego, CA), which will primarily target the quadriceps followed by the hip extensors and plantarflexors. The equipment allows for partial gravity-elimination that can be tailored to each participant depending on his/her initial level of capability. The sled can be positioned from nearly horizontal to approximately a 30 degree incline (Figure 3). Weights will be added to a weight bar to increase resistance. Target load will be 40% to 80% of 1-repetition maximum (1RM) with progression towards 80% according to the NSCA resistance training guidelines for muscle power training (Faigenbaum, 2009). Participants will undergo 1RM testing prior to the first intervention session in order to determine the initial training load. This session will occur a minimum of 48 hours prior to the first intervention session. Our pilot subjects were able to begin training with initial loads varying between 50 to 60% of 1RM. Actual loads will be determined by accounting for the angle of inclination of the sled and multiplying the load by the sine of the angle. Following the warm-up, each participant will perform 3 to 5 submaximal efforts followed by 6 sets of 5 maximum-effort repetitions at the predetermined percentage of 1RM for each leg separately. Instructions for the concentric phase of the leg press will be to "push as fast as possible" with the eccentric portion performed slow and controlled over 1-2 seconds. Performing the concentric

[figure not shown]

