Adverse events will be collected from the start of treatment through the end of study participation. All adverse events regardless of attribution to treatment procedures will be collected and recorded. Participants will be asked in an open-ended way about the presence of any adverse events. The likelihood that the event is related or not related to treatment will be noted. Reporting of adverse events will use a grading and attribution scale (Grading = mild, moderate, severe; Attribution = Definite, Probable, Possible, Unlikely, Unrelated). Serious Adverse Events that occur to participants will be reported to the LSUHSC and Seattle Children's IRB immediately. Should an unanticipated adverse event or outcome be discovered, [name] or [name] will notify their respective IRB within 48 hours and proceed accordingly. Should there be a serious adverse event that occurs that increases the risks to the participants, the study will be stopped, an investigation will be conducted, and a findings report will be generated before the study is resumed. This study is a clinical trial with a relatively small number of participants in a vulnerable population (children with cerebral palsy). The experimental intervention and the comparison intervention propose low risk to the participants. [name] will also monitor the data for any inconsistencies or outliers.

Data Safety Monitoring Board (DSMB): For this trial, we propose a 3-member DSMB. [name] has agreed to serve as the chair of the DSMB, in order to provide an unbiased assessment. This study is a clinical trial with a relatively small number of participants in a vulnerable population (children with cerebral palsy).

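### Adverse event collection starts at treatment, after baseline and 1RM testing, so the plan does not require non-serious events from that testing to be recorded

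*Combined protocol and SAP*

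**What the plan says.** The collection rule is in Data Safety Monitoring: "Adverse events will be collected from the start of treatment through the end of study participation". The next sentence makes the scope broad within that window: "All adverse events regardless of attribution to treatment procedures will be collected and recorded". Participants are asked an open-ended question, and each event is graded for severity and for its relation to treatment on a five-level scale.

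Two sets of physical tests come before treatment. Under Intervention Protocols, both arms have the same 1RM session: "Participants will undergo 1RM testing prior to the first intervention session in order to determine the initial training load", and "This session will occur a minimum of 48 hours prior to the first intervention session". Under Testing / Assessment Protocols, "Outcomes will be assessed pre and post intervention to determine immediate effects of treatment". For timing, "The goal will be to perform the baseline assessment within 1 week prior to the start of the intervention", with at least 48 hours kept clear of any training session, although "a 2-week window will be allowed for all assessment timepoints". The Muscle Performance item of that assessment includes isokinetic dynamometry of the knee extensors and ankle plantarflexors at full effort, plus power and strength tests on the leg press.

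Risks to Participants says: "There is a mild risk of temporary delayed-onset muscle soreness from walking, power and strength training and testing". The same sentence adds joint pain, chiefly at the knees. That section also has the intervention therapist watch for soreness, joint pain, falls and discomfort at both training and testing sessions.

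**The concern.** The protocol names testing as a source of harm, yet starts collecting adverse events only after the first round of testing is over. A child whose knee hurts after the dynamometer or the 1RM session, and who recovers before session 1, falls outside the stated rule. A child whose pain persists may first report it once treatment has begun, when the form asks how likely it is to be related to treatment and nothing earlier shows when it started.

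Two things are at stake. One is whether the trial's safety record covers all of its own procedures in children, a group the protocol itself describes as vulnerable. The other is whether events recorded early in treatment can be attributed correctly.

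**Working it through.** The documents give no event rate or safety figure to reproduce, so the check sets the timings side by side.

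1. **Start of the window.** Data Safety Monitoring starts collection at the start of treatment. No section starts it at consent, enrolment or first study procedure.

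2. **1RM session.** It is at least 48 hours before session 1 in both arms. No upper limit on the gap is stated.

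3. **Baseline assessment.** It is also at least 48 hours before session 1. The target is within 1 week, and a 2-week window is allowed.

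4. **Uncovered interval per child.** This is the start of treatment minus the time of testing. The minimum is 48 hours after either test. For baseline testing it runs up to 1 week on target, or up to 2 weeks if the allowance is read as time before treatment.

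5. **Exposure.** All 48 planned children have both tests. If 1RM testing is combined with the baseline visit, there are 48 × 1 = 48 child-sessions before the window opens. If the two are separate, there are 48 × 2 = 96. The protocol speaks of a 1RM session but does not say whether it may share a visit with the assessment, which also includes leg-press strength testing.

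6. **Does the monitoring text close the gap?** Not fully. Risks to Participants provides observation at testing sessions but does not say that what is seen is recorded as an adverse event. The soreness it names is delayed in onset, so it may appear after the session ends. The task is given to the intervention therapist, whereas Outcome Measures has assessors who are blinded to group, so it is unclear who observes at baseline.

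7. **Do the reporting routes close it?** In part. The sentences on serious and on unanticipated events carry no start date, so those events reach the IRBs whenever they occur. The DSMB text sends adverse events to the IRBs and has the board review those reported. For ordinary events, this depends on their having been collected.

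8. **Later testing.** The post-treatment, 2-month and 6-month assessments fall inside the window. Only the pre-treatment round is outside it.

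Baseline StepWatch and GPS wear is a smaller case of the same kind. It lasts 7 days, and skin problems and intolerance are listed as risks. If it is done as part of the baseline assessment, it falls largely or wholly before treatment.

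**The case against.** The strongest reply is that little is lost. Serious or unanticipated injuries have a route to the IRBs at any time. The interval is short, a therapist is assigned to watch testing sessions, and soreness that persists can surface under the open-ended question at session 1. The attribution scale runs down to unrelated, so carried-over pain need not be charged to training. The protocol also reports that soreness and joint pain were minimal in earlier maximal testing and that joint injury was rare. Finally, the start of treatment is not defined, and the 1RM session is described under Intervention Protocols.

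Most of this stands, and it limits the point to expected, non-serious events before session 1. It does not remove the point. These are the events that Risks to Participants anticipates. The attribution scale helps only if the date of onset is known, and no pre-treatment record is required to supply it. On the undefined term, the protocol places 1RM testing before the first intervention session, so the natural reading leaves it outside the window.

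A reader might infer three stronger things that the documents do not support:

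- **That testing injuries are never recorded or never reach the IRBs or DSMB.** The undated reporting sentences and the monitoring of testing sessions contradict this.
- **That the gap biases the comparison of arms.** Both arms have the same pre-treatment testing, and no reason for differential misattribution appears in the text.
- **That a number of lost events can be stated.** The documents give no rate for testing-related events, the number of sessions is uncertain by a factor of two, and some events would be caught by the routes above.

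**Conclusion.** The point holds in a limited form. As written, the collection window opens after the baseline and 1RM testing, so recording of non-serious events from those procedures is not required. Events that continue into treatment would have no earlier record to inform their attribution. This affects the completeness and attribution of safety data in both arms alike. It touches no efficacy outcome or planned efficacy analysis.

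The size can be given only as exposure: 48 children, with the interval and the 48 to 96 child-sessions worked out above. The conclusion rests on reading the start of treatment as the first intervention session. If the sponsor means it to include the 1RM session, the gap narrows to baseline assessments held before that session, and the definition should be written down. The change is worth making: the expected events are mostly mild, but the trial should record harms from its own procedures in children.

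**What to change.** In Data Safety Monitoring, start collection at the first study procedure, defined as the baseline assessment or 1RM testing, whichever comes first, and leave the end of the window as it is. Record onset dates, and tabulate events before session 1 separately from treatment-period events. The Data Analysis Plan section currently describes no adverse event table, so a sentence there would suit. Reconcile Risks to Participants with this rule by stating that findings from testing sessions go on the adverse event form, and who completes it at baseline.

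The cost is one changed phrase, a short addition to the analysis text, and a slightly longer collection period on the existing forms. No new visits or staff are needed.

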Power Calculations: The sample size calculations for Specific Aim 1 focus on assessing differences in changes from baseline to 8 weeks in mean outcome between the PT3 and control groups. Estimates of variability and clinically relevant effect sizes for Specific Aims 1 & 2 were obtained from preliminary data for the treatment effect estimates and from [name] et al. (2013) for the comparison group effect estimates. Assuming a statistical model for a replicated randomized complete block experiment with fixed treatment factor (PT3 vs comparison) and a 0.050 two-sided significance level, the null (primary) hypothesis of no difference in mean change from baseline to 8 weeks in self-selected gait speed between groups will have 90% power to detect a difference of 0.12 m/s given a common standard deviation of 0.167 m/s with a sample size of n=24 per group. A sample size of 24 in each group will also have 79% power to detect a difference of 0.137 m/s in fast gait speed, assuming a common standard deviation of 0.127 m/s. Specific Aim 2: A sample size of 24 in each group will have 99% power to detect a difference in mean peak power of 0.819 watts/kg with a common standard deviation of 0.485 watts/kg with a 0.050 two-sided significance level. A sample size of 24 in each group will have 90% power to detect a difference in mean fascicle length of 1.55 cm given a common standard deviation of 1.61 cm. Specific Aim 3: Average number of strides per day (over a 5 day period) were obtained from [name] et al. (2014) with the differences observed between GMFCS levels II and II used to approximate the expected differences between treatment groups. Assuming a common standard deviation of 1,580 average strides/day, a sample size of 24 will have 90% power to detect a difference in average strides/day between treatment groups as small as 1,510 strides/day. In the event that we experience dropout, the primary analysis of each aim will still have > 80% power to accommodate as high as a 25% dropout rate (n=19 per group).

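### The 90% power stated for self-selected gait speed does not follow from its own inputs, which give about 68%; the two gait-speed SDs appear to be transposed

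*Combined protocol and SAP*

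**What the plan says.** All the inputs stand in the Power Calculations paragraph of the combined protocol and SAP. The model has a "fixed treatment factor (PT3 vs comparison) and a 0.050 two-sided significance level", and the primary null hypothesis is "no difference in mean change from baseline to 8 weeks in self-selected gait speed between groups". For that hypothesis the trial "will have 90% power to detect a difference of 0.12 m/s given a common standard deviation of 0.167 m/s with a sample size" of 24 per group. With the same group size, the plan claims "79% power to detect a difference of 0.137 m/s in fast gait speed, assuming a common standard deviation of 0.127 m/s".

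The paragraph goes on to give power for peak power, fascicle length and strides per day, all at 24 per group. It ends by saying that the primary analysis of each aim keeps more than 80% power with dropout of up to 25%, given as 19 per group.

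The Data Analysis Plan names the primary model: a general linear model on change from baseline, with site and GMFCS level as fixed blocking factors. Neither section states a variance reduction from blocking or a correlation between baseline and follow-up.

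**The concern.** The two gait-speed statements cannot both be right. At the same sample size, alpha and model, power rises with the ratio of difference to SD. That ratio is 0.12/0.167 = 0.72 for self-selected speed and 0.137/0.127 = 1.08 for fast speed. Yet the smaller ratio is given 90% power and the larger one 79%.

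The self-selected figure is the justification for enrolling 48 children on the primary hypothesis. Taken as printed, it understates the risk of a false negative for the planned effect by a factor of about three. If instead the SDs were exchanged when the paragraph was written, the design stands, but the plan records the wrong SD for its primary outcome.

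**Working it through.** **Inputs** (all from Power Calculations): two-sided alpha 0.05; n = 24 per group; the differences and SDs in the table below.

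**Formula.** Two-sample t-test with noncentrality λ = Δ / (SD × √(2/n)) and 2n − 2 = 46 degrees of freedom. The critical value is 2.013, and √(2/24) = 0.2887. Power is the probability that a noncentral t with parameter λ exceeds 2.013; the opposite tail is negligible.

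**Step 1. Does the formula reproduce the plan's other figures?**

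| Outcome | Δ / SD | λ | Power | Stated |
|---|---|---|---|---|
| Fascicle length (cm) | 1.55 / 1.61 | 3.34 | 90.4% | 90% |
| Strides/day | 1,510 / 1,580 | 3.31 | 90.0% | 90% |
| Peak power (W/kg) | 0.819 / 0.485 | 5.85 | >99.9% | 99% |

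It does, so the method matches the plan's.

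**Step 2. The two gait-speed statements as printed.**

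| Outcome | Δ / SD (m/s) | λ | Power | Stated |
|---|---|---|---|---|
| Self-selected (primary) | 0.12 / 0.167 | 2.49 | 68.3% | 90% |
| Fast | 0.137 / 0.127 | 3.74 | 95.5% | 79% |

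For the primary outcome, other conventions do not close the gap: the normal approximation gives 70.2%, a one-sided alpha of 0.05 gives 79.0%, and reading n as 48 per group gives 93.6%.

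**Step 3. Exchange the SDs.**

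| Outcome | Δ / SD (m/s) | λ | Power (t) | Power (normal) | Stated |
|---|---|---|---|---|---|
| Self-selected | 0.12 / 0.127 | 3.27 | 89.3% | 90.5% | 90% |
| Fast | 0.137 / 0.167 | 2.84 | 79.4% | 81.1% | 79% |

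Solving the other way, the SD that gives exactly 90% for a difference of 0.12 m/s is 0.1255, and the SD that gives 79% for 0.137 m/s is 0.168. Each is close to the SD printed for the other outcome.

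**Step 4. Could blocking explain it?** Fitting site and a three-level GMFCS factor leaves 43 error degrees of freedom and gives 68.2% and 95.5%, essentially unchanged. To reach 90% for the primary outcome, blocking would have to remove 1 − (0.1255/0.167)² ≈ 43% of the variance of change. To bring fast speed down to 79%, the variance would have to rise by a factor of (0.168/0.127)² ≈ 1.75. One model cannot plausibly do both.

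**Step 5. The dropout sentence as a further check.** At 19 per group the primary outcome has 57.8% power with SD 0.167 and 80.9% with SD 0.127. Only the second agrees with the claim of more than 80%. The sentence also has a slip of its own: 19 of 24 is a loss of 5/24 = 20.8%, whereas 25% loss leaves 0.75 × 24 = 18. At 18 per group the primary outcome has 78.6% (SD 0.127) or 55.4% (SD 0.167), below 80% either way.

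**Step 6. What follows if SD 0.167 is right.** Reaching 90% power needs 42 per group and 80% needs 32. With 24 per group, the difference detectable with 90% power is 0.160 m/s. That is as large as the whole pre-to-post gain reported for the PT3 pilot (0.16 m/s, Preliminary Studies).

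**The case against.** The mismatch itself cannot be argued away; even the most favourable rounding of the printed inputs (0.1249/0.1665) gives only 72%. The better objection concerns its consequence. If the SDs are merely transposed, the design has about 89% power, 48 participants are adequate, and no analysis or procedure changes. The 32% risk of a missed effect exists only on the less likely reading, and the n = 19 statement favours the benign one. All of that stands, and the size of the problem should be described accordingly.

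Two further cautions are fair. No single method returns both printed powers exactly after the exchange, so the agreement is to within about one point. Transposition also remains an inference, since the pilot and 2013 trial data are not in the documents.

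A different defence reads 0.167 as the SD at a single time point and not of the change. Power would then be 68%, 78%, 88% and 97% at assumed pre-post correlations of 0.5, 0.6, 0.7 and 0.8, so a correlation a little above 0.7 would give 90%. The plan states no such correlation, and this reading leaves the fast-speed figure unexplained.

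**Conclusion.** The concern holds. As printed, the primary power statement is wrong by about 22 percentage points (68.3% against 90%) and the fast-speed statement by about 16 in the other direction (95.5% against 79%). This rests only on figures in the paragraph and on a two-sample t-test that reproduces its other three power statements.

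The most probable explanation is that the two SDs were exchanged. The errors run in opposite directions, one exchange repairs both, and the claim at 19 per group is true for the primary outcome only with SD 0.127. On that reading the true power is about 89% and the sample size is sound. The documents cannot settle which SD belongs to which outcome, and because this sentence supports the primary sample size, it has to be resolved and not left as printed.

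**What to change.** Check both gait-speed SDs against the pilot data and the 2013 trial, then correct the Power Calculations paragraph in one of two ways:

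- **If transposed:** print SD 0.127 m/s for self-selected speed (power about 89%) and 0.167 m/s for fast speed (about 79%). The sample size stands.
- **If the printed SDs are right:** restate power as about 68% for self-selected speed and about 96% for fast speed. The sponsor should then say openly whether 48 participants is still accepted, given that 90% power would need 42 per group.

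In either case re-derive the dropout sentence with the confirmed SD, and make the percentage and the group size agree (20.8% for 19 per group, or 18 per group for 25%).

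The cost is a look-up in existing data and a correction to one paragraph. Randomisation, outcomes and the analysis model are untouched. In the less favourable case, the price is a lower stated power for the primary outcome.
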